### **15.1.1. TEAES**

Incidence of TEAEs will be presented by SOC and PT, with SOC in alphabetical order and PT in order of decreasing frequency. The incidence of TEAEs will be broken down further by maximum severity and maximum relationship to study treatment.

#### **15.1.1.1. Severity**

Severity is classed as mild/ moderate/ severe (increasing severity). TEAEs with a missing severity will be classified as severe. If a participant reports a TEAE more than once within that SOC/ PT, the AE with the worst case severity will be used in the corresponding severity summaries.

#### **15.1.1.2. Relationship to Study Treatment**

Relationship, as indicated by the Investigator, is classed as ‘unrelated’, ‘unlikely to be related’, ‘possibly related’, and ‘probably related’ (increasing severity of relationship). A ‘related’ TEAE is defined as a TEAE with a relationship to study treatment as ‘possibly related’ or ‘probably related’ to study treatment. TEAEs with a missing or ‘unknown’ relationship to study treatment will be regarded as ‘related’ to study treatment. If a participant reports the same AE as both related and unrelated within that SOC/ PT, the related AE will be used in the corresponding relationship summaries.

### **15.1.2. TEAES LEADING TO DISCONTINUATION OF STUDY TREATMENT**

TEAEs leading to permanent discontinuation of study treatment will be identified by using the ‘Action taken with study treatment’ variable equal to ‘Drug Withdrawal’ from the Adverse Events eCRF. A summary of TEAEs leading to discontinuation of study treatment by SOC and PT will be prepared. A listing of all TEAEs leading to

---

Document:

Author:

Version Number:

2.0

Version Date:

23APR2024

Template No.: CS\_TP\_BS016 Revision 6

Reference: CS\_WI\_BS005

Effective Date: 02Dec2019

Copyright © 2009, 2010, 2012, 2016, 2018, 2019 [REDACTED]. All rights reserved. The contents of this document are confidential and proprietary to [REDACTED] and its subsidiaries. Unauthorized use, disclosure or reproduction is strictly prohibited.

discontinuation of study treatment will be provided, along with the details as to whether the event was related or was serious.

#### **15.1.3. SERIOUS ADVERSE EVENTS**

Serious adverse events (SAEs) are those events recorded as 'Serious' on the Adverse Events eCRF. A summary of serious TEAEs by SOC and PT will be prepared.

#### **15.1.4. ADVERSE EVENTS LEADING TO DEATH**

TEAEs leading to death are those events that are recorded as 'Fatal' on the Adverse Events eCRF. A summary and listing of TEAEs leading to death by SOC and PT will be prepared.

#### **15.1.5. EVENTS OF CLINICAL INTEREST**

ECIs, as defined in section 8.4.5 of the protocol, are those events recorded as 'ECIs' on the Adverse Events eCRF. A summary of TEAEs of Clinical Interest by SOC and PT will be prepared.

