8.4.5 Events of Clinical Interest

Selected nonserious AEs and SAEs are also known as ECIs and must be reported to the Sponsor.

Events of clinical interests for this study that require regulatory reporting **within 24 hours** of learning of the event include:

- An elevated AST or ALT lab value that is greater than or equal to $3 \times$ the upper limit of normal (ULN) and an elevated total bilirubin lab value that is greater than or equal to $2 \times$ ULN and, at the same time, an alkaline phosphatase lab value that is less than $2 \times$ ULN, as determined by way of protocol-specified laboratory testing or unscheduled laboratory testing.*

***Note:** These criteria are based upon available regulatory guidance documents. The purpose of the criteria is to specify a threshold of abnormal hepatic tests that may require an additional evaluation for an underlying etiology. The study site guidance for assessment and follow-up of these criteria can be found in the Investigator Study File Binder (or equivalent).

- ATE (including myocardial infarction, stroke, or peripheral arterial events) and VTE (including pulmonary embolism and deep venous thrombosis).

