9.4.3 Safety Analysis

The APaT population will be used for all safety analyses.

Safety and tolerability will be assessed by clinical review of all relevant parameters including AEs, laboratory values, vital signs, and body weight.

For the analysis of safety data, the following conventions will be used:

- Baseline will be defined as the last measurement before the first study drug intake.
- The on-treatment period will be defined as the period from the day of first tablet intake up to and including the day of last active study drug intake, extended by 14 days. However, any delayed events or diagnoses judged by the Investigator to be related to study drug will also be considered to have occurred on-treatment and will be included in the safety analysis.
- Last measurement is the last value obtained during the on-treatment period.

The proportion of participants with prespecified events listed as ECIs described in Section 8.4.5 during the on-treatment period will be provided along with corresponding 95% Clopper-Pearson CIs. All ECIs will be summarized, even if the incidence is zero.

In addition, the broad AE categories consisting of the percentage of participants with any AE, a drug-related AE, a serious AE, an AE, which is both drug-related and serious, and who discontinued study drug due to an AE will be summarized with corresponding 95% Clopper-Pearson CIs (Table 10). On-treatment AEs are those occurring from first intake of study drug to 14 days after intake of the last active tablet of study drug. AEs occurring during the designated pre-treatment (between V1 and first intake of study drug) and post-treatment (>14 days after last tablet intake of study drug) periods will be provided.

Table 10 Analysis Strategy for Safety Parameters

Safety Endpoint ^a	Within Group 95% CI ^b	Descriptive Statistics
Any AE	X	X
Any Serious AE	X	X
Any Drug-Related AE	X	X
Any Serious and Drug-Related AE	X	X
Discontinuation due to AE	X	X
Specific AEs, SOCs, ECIs, and PDLCs (incidence ≥ 4 participants)		X
Specific AEs, SOCs, ECIs, and PDLCs (incidence < 4 participants)		X
Change from Baseline Results (laboratory tests, vital signs)		X

Abbreviations: AE=adverse event; CI=confidence interval; ECI=event of clinical interest; PDLC=Predefined Limit of Change; SOC=System Organ Class; X=results will be provided.

a. AE references refer to both clinical and laboratory AEs.

b. 95% CIs will be calculated using the Clopper-Pearson method.

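### SAP 15.1.5 plans a SOC/PT summary of eCRF-flagged ECIs and does not specify the ECI proportions, 95% CIs or zero-incidence reporting promised in protocol 9.4.3; SAP 3.2 does not declare the change

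*SAP*

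**What the plan says.** **Protocol 8.4.5** defines the ECIs as conditions. One is a hepatic laboratory combination: raised AST or ALT, "an elevated total bilirubin lab value that is greater than or equal to" 2 × ULN, and alkaline phosphatase below 2 × ULN. The other bullet is "ATE (including myocardial infarction, stroke, or peripheral arterial events) and VTE (including pulmonary embolism and deep venous thrombosis".

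**Protocol 9.4.3** commits to an analysis of them: "The proportion of participants with prespecified events listed as ECIs described in Section 8.4.5 during the on-treatment period will be provided", and these "will be provided along with corresponding 95% Clopper-Pearson CIs". It adds: "All ECIs will be summarized, even if the incidence is zero". Table 10 in the same section has a row "Specific AEs, SOCs, ECIs, and PDLCs (incidence ≥ 4 participants" that is marked for descriptive statistics only, with no interval.

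**SAP 15.1.5** refers to protocol 8.4.5 for the definition, but then says that ECIs "are those events recorded as" ECIs on the adverse event eCRF. The one output it plans is: "A summary of TEAEs of Clinical Interest by SOC and PT will be prepared".

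**SAP 3.2** lists the changes from the protocol, down to a corrected footnote in the visit-window table. It does not mention the ECI analysis. Protocol 9.4 says that the SAP prevails where the two differ.

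**The concern.** Efficacy and PK analyses have been dropped, so safety is what this report is for (SAP 1 and 3.2). Thromboembolism runs through the protocol: a history of it is an exclusion (5.2), an occurrence is a mandatory reason to stop study drug (7.2), and it is an ECI with 24-hour reporting (8.4.5).

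The SAP replaces a proportion for a defined condition by a table of coded terms. A SOC/PT table counts participants per preferred term. It does not state how many women had any VTE or any ATE, because a woman with both deep vein thrombosis and pulmonary embolism sits in two rows.

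The SAP also treats the protocol definition and the site's flag as the same thing, and plans no comparison between them. Because the SAP prevails, the protocol's promise lapses without being declared.

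**Working it through.** The plan gives no figure here to reproduce. The check is a comparison of texts, followed by short illustrations of what the promised analysis would report.

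**1. Promise against plan**

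| Element | Protocol 9.4.3 | SAP |
|---|---|---|
| Unit of summary | Participants with the ECIs of 8.4.5 | SOC and PT (15.1.5) |
| Identification | Definition in 8.4.5 | Definition cited, then eCRF flag (15.1.5) |
| Interval | 95% Clopper-Pearson in the text; none for ECIs in Table 10 | None stated; SAP 8 gives counts and percentages for categorical data |
| Zero incidence | Reported | Not stated |
| Declared as a change | – | Not in 3.2 |

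Under SAP 8, percentages per preferred term are to be expected. A proportion for each ECI as defined in 8.4.5 is not specified.

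**2. Where an unflagged case would go**

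- A treatment-emergent VTE or ATE without the flag still enters the all-TEAE table (SAP 15.1.1) and the AE listings (15.1). It also enters the serious TEAE table if serious (15.1.3), and the discontinuation outputs if the action taken was drug withdrawal (15.1.2). It is missing from the ECI table.
- A hepatic case is largely found from laboratory data through the Hy's Law components in SAP Table C, with no flag needed. Two gaps remain. SAP 15.3 reports central-laboratory results, while 8.4.5 also counts unscheduled testing. Table C uses bilirubin >2 × ULN, while 8.4.5 uses ≥2 × ULN.

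**3. What a reported zero would say**

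With no events in n women, the exact 95% upper limit is 1 − 0.025^(1/n). The number treated before early termination is not given, so n is an assumption. The top of the range is the planned allocation of 1,878.

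| n (assumed) | Upper limit for 0/n |
|---|---|
| 100 | 3.62% |
| 250 | 1.47% |
| 500 | 0.74% |
| 1,000 | 0.37% |
| 1,878 | 0.20% |

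**4. Why term rows cannot stand in for a VTE row**

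Suppose one woman in 500 has both deep vein thrombosis and pulmonary embolism. Counted once, the result is 1/500 = 0.20% (95% CI 0.005% to 1.11%). A reader who adds the two term rows gets 2/500 = 0.40% (0.05% to 1.44%).

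**5. Is zero plausible?**

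The documents state no absolute VTE rate. The full planned exposure of 16,500 cycles is 16,500 × 28 / 365.25 = 1,265 woman-years. Assumed rates of 0.5, 1 and 2 per 1,000 woman-years give 0.63, 1.26 and 2.53 expected cases, and Poisson probabilities of no case, exp(−expected), of 53%, 28% and 8%. Shorter exposure after early termination would make zero more likely.

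**The case against.** The strongest reply is that little information would be lost.

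- **Other outputs carry the events.** As shown in the working, an unflagged VTE or ATE that is a TEAE appears elsewhere, and with so few cases a reader could cross-check. This stands. A reader might infer that unflagged events vanish from the report; the SAP does not support that.
- **A participant count may exist.** SAP 15.1 plans an overview of number and percentage of participants for the categories in its sub-sections, and ECIs are one of these. An any-ECI row is therefore possible, although ECIs are not among the broad categories then named. This stands in part: such a row would pool thromboembolism with liver values and give no VTE or ATE proportion.
- **Zero rows may be in the templates.** SAP 8 leaves format and content to output templates, which were not available for this review. SAP 15.1.5 is silent on zeros; it does not exclude them. A reader might infer that zeros will be suppressed, but that cannot be shown.
- **The protocol does not ask for these exact rows.** It puts ATE and VTE in one bullet, names no term list, and its Table 10 treats ECIs descriptively. This is fair. Separate rows and a term list are a way to carry out the 9.4.3 text, not a quotation of it.
- **There is no evidence of under-flagging**, and ECIs require reporting within 24 hours. This also stands. The point does not depend on sites having missed flags.

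None of this supplies the interval, states the zero rule, or explains why SAP 3.2 is silent.

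**Conclusion.** The point holds as a gap in specification. For the ECIs of protocol 8.4.5, the SAP text does not specify the participant proportion, the Clopper-Pearson interval or the zero-incidence reporting promised in 9.4.3. It defines no participant-level VTE or ATE count, identifies ECIs by the eCRF flag alone, and does not declare the change. It should be corrected, because it concerns a principal safety summary in a report that is now safety-only.

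The size is modest. The individual events remain visible; what is missing is the correct count of women and its uncertainty. The limits in the working depend on an assumed number treated, and the expected counts on assumed rates at full planned exposure. It may be tempting to say that one missed or double-counted case would be a large fraction of all VTE. That would rest on those assumed rates and on a flagging or adding error for which the documents give no evidence, so it is not part of this conclusion.

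**What to change.** Replace the output rule in SAP 15.1.5 with wording such as:

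> The number and proportion of SAF participants with at least one on-treatment (a) VTE, (b) ATE and (c) hepatic ECI will be shown as three fixed rows, including zero counts, with 95% Clopper-Pearson CIs. Events are identified by the eCRF ECI flag, by a list of VTE and ATE preferred terms agreed before database lock, or by laboratory values meeting protocol 8.4.5. Discrepancies between flag and derived status will be listed.

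Keep the SOC/PT table as supporting detail. In addition:

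- Reconcile the text of protocol 9.4.3, which gives ECIs an interval, with its Table 10, which does not.
- Reconcile the bilirubin cut-off in SAP Table C (>2 × ULN) with protocol 8.4.5 (≥2 × ULN).
- Record in SAP 3.2 anything in the protocol's ECI analysis that is deliberately dropped.

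The cost is SAP wording, a short term list and one small table from data already collected. The downside is that a few unflagged events may enter the ECI count and need a clinical check.

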### **15.2. DEATHS**

A listing of all fatal TEAEs will be provided. Details of the death as recorded on the Death Details eCRF will be presented in an appendix data listing.

### **15.3. LABORATORY EVALUATIONS**

Results from the central laboratory will be included in the reporting of this study for hematology, biochemistry, and urinalysis. A list of laboratory assessments to be included in the outputs is included in Appendix 3 of the protocol (Table 10). For each parameter, normal reference ranges and safety ranges will be presented.

Presentations will use International System of Units (SI). Results will be converted as needed prior to the analysis. Quantitative laboratory measurements reported as '< X', i.e., below the lower limit of quantification (LLQ), or '> X', i.e., above the upper limit of quantification (ULQ), will be converted to X for the purpose of quantitative summaries, but will be presented as recorded, i.e., as '< X' or '> X' in the listings.

Document:

Version Number:

2.0

Version Date:

23APR2024

Template No.: CS\_TP\_BS016 Revision 6

Reference: CS\_WI\_BS005

Effective Date: 02Dec2019

Copyright © 2009, 2010, 2012, 2016, 2018, 2019 [REDACTED]. All rights reserved. The contents of this document are confidential and proprietary to [REDACTED]. Unauthorized use, disclosure or reproduction is strictly prohibited.

Actual and change from baseline in laboratory test values will be summarized by visit (including Baseline and last measurement) under each of hematology, biochemistry, and urinalysis. All available lab data will be included in the data listings.

In addition, markedly abnormal liver function-related laboratory tests will be summarized during all visits in the study based on the criteria listed below in Table C.

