8.3.4 Clinical Safety Laboratory Assessments

See [Appendix 3](#) for the list of clinical laboratory tests to be performed and the SoA (Section 1.3) for the timing and frequency.

The Investigator or medically qualified designee (consistent with local requirements) must review the laboratory report, document this review, and record any clinically relevant changes occurring during the study in the AE eCRF. The laboratory reports must be filed with the source documents.

All protocol-required laboratory assessments, as defined in [Appendix 3](#) must be conducted in accordance with the laboratory/procedure manual and the SoA.

If laboratory values from nonprotocol-specified laboratory assessments performed at the institution's local laboratory require a change in study participant management or are considered clinically significant by the Investigator (eg, SAE or AE), then the results must be recorded in the appropriate eCRF.

For any laboratory tests with values considered clinically significantly abnormal during participation up to EOS. Every attempt should be made to perform repeat assessments until the values return to normal or baseline or if a new baseline is established as determined by the Investigator. If such values do not return to normal/baseline within a period of time judged reasonable by the Investigator, the etiology should be identified, and the Sponsor notified.

Screening laboratory safety tests may be repeated once before treatment allocation (V2) at the discretion of the Investigator if the initial results are inconsistent with the participant's clinical

status or recent laboratory results. Screening may be performed between 7 days and 42 days before V2.

Laboratory safety tests (hematology and biochemistry) are scheduled to be repeated at V7 for all participants. If the participant discontinues early from the protocol-specified Treatment Period, those safety tests specified for the EOS Visit (V7) should be completed.

Details on sampling, processing, and shipping of the materials to the central laboratory will be described in a separate laboratory/procedure manual.

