For continuous measures such as changes from baseline in laboratory tests and vital sign parameters, summary statistics for on-treatment values will be provided in table format at V2 and V7.

For summary statistics of laboratory parameters and vital signs per visit, visit windows as described in [Table 11](#) will be used.

Table 11 Timeframe Used in the Analysis of Vital Signs and Laboratory Parameters

Definition	Visit	Visit window (treatment day)
Baseline	V1 Screening	<1
In-treatment ^a	V3 After Cycle 1	29 \pm 28 days
	V4 After Cycle 4	113 \pm 28 days
	V5 After Cycle 7	197 \pm 28 days
	V6 After Cycle 10	281 \pm 28 days
	V7 After Cycle 13	379 \pm 28 days
	Last measurement	>1

Abbreviation: V=Visit

a. From Day 1 until ≤ 28 days after last tablet intake; Day 1 is defined as day of first study drug intake

Values outside these visit windows, or outside the defined in-treatment period for post-baseline assessments, will be excluded from the analysis of that particular visit.

However, these visit windows will only be applied for analyses performed per visit; no values will be excluded from the determination of markedly abnormal laboratory or vital signs values

(unless outside the defined in-treatment period). If more than one observation is available within a specific visit window, the latest value will be used for analysis.

9.4.3.1 *Adverse Events*

An overview table of the number (percentage) of participants with any AEs, SAE, drug-related AEs, any serious drug-related AEs, any discontinuation due to AE, any discontinuation due to a SAE, any discontinuation due to a drug-related AE, any discontinuation due to serious drug-related AE, and any deaths will be presented for the on-treatment period. Pre-treatment AEs/SAEs starting before the in-treatment period will be excluded from the AE analyses (unless there is an increase in Investigator assessed intensity or causality, or the AE meets SAE criteria post-treatment allocation) and reported in separate frequency tables with the methods described above.

The number (percentage) of participants with at least one AE will be presented in a frequency table of Medical Dictionary for Regulatory Activities (MedDRA) system organ class (according to the primary path) and MedDRA preferred term. The same tables will be presented by relationship to study drug (“Related” and “Not related”) by the Investigator; and by severity of the AE (“mild”, “moderate”, “severe”).

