All participants who prematurely discontinue from treatment due to an AE will be summarized considering all their AEs for which the action taken on study drug was “drug withdrawn”. The summary will be performed by MedDRA system organ class, preferred term, and relationship.

9.4.3.2 *Laboratory Parameters*

Routine hematology and biochemistry parameters measured at V1 (Screening) and V7 (EOS or ET) will be determined by a central laboratory, unless the central laboratory results are not available in time for either starting study treatment administration and/or response evaluation. The sexually transmitted infections (STI) panel testing will be performed by a local laboratory. The measurements of each laboratory parameter will be converted to Standard International units before the statistical analysis, unless otherwise specified. The conversion factors will be recorded in the database.

For each parameter, normal reference ranges (including the date of effect) and safety ranges will be presented. Safety ranges are defined on the suggestions of the FDA. If safety ranges are not available for specific parameters, in-house criteria will be used and presented.

Summary Statistics

For each laboratory parameter, summary statistics will be calculated by assessment (V1, V7, and last measurement, respectively). In addition, summary statistics will be presented for the change from baseline. Shifts from baseline to V7 and last measurement will be presented based on shift categories to be identified in the SAP. The incidence of post-baseline markedly abnormal values will be presented based on categories to be identified in the SAP.

9.4.3.3 *Vital Signs and Body Weight*

Blood pressure and body weight measurements will be performed at screening (V1), treatment allocation (V2), and after Cycles 1, 4, 7, and 10 and at the EOS.

Summary Statistics

For each parameter (including calculated BMI), descriptive statistics will be calculated by visit (including last measurement). In addition, the summary statistics will be presented for the change from baseline. The incidence of post-baseline markedly abnormal values will be presented based on categories to be identified in the SAP.

9.4.3.4 *Physical, Gynecological, and Breast Examinations*

Clinically significant findings of general physical, gynecological, and breast examinations performed at EOS will be recorded as AEs by the Investigator; these findings will be recorded in the AEs eCRF.

9.4.4 *Other Analysis*

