## 6.5. WINDOWING CONVENTIONS

The on-treatment period for safety assessments will be defined as the period from the day of the first tablet intake up to and including the day of the last tablet intake, extended by 14 days after last tablet.

Windows shown in Table B will be used in the analysis of vital signs and laboratory parameters for analyses performed per visit. Values outside these visit windows, or outside the defined on-treatment period for post-baseline assessments, will be excluded from the analysis of that particular visit. However, no values will be excluded from listings or for the determination of markedly abnormal laboratory (unless outside the defined in-treatment period). If more than one observation is available within a specific visit window, the latest value will be used for analysis.

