**Table B Timeframe Used in the per Visit of Vital Signs and Laboratory Parameters**

Definition	Visit	Visit window (treatment day)
Baseline	Visit 1 Screening	<1
On-treatment a	Visit 3 After Cycle 1	29 ± 28 days
	Visit 4 After Cycle 4	113 ± 28 days
	Visit 5 After Cycle 7	197 ± 28 days
	Visit 6 After Cycle 10	281 ± 28 days
	Visit 7 After Cycle 13	379 ± 14 days
	Last measurement	>1

a. From Day 1 until ≤14 days after last tablet intake; Day 1 is defined as day of first study treatment intake.

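### SAP 15.3 lets pre-drug screening values into the markedly abnormal liver summary, and the 14-day cut-off behind SAP 6.5 drops most of the V7 window

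*SAP*

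**What the plan says.** SAP 15.3 sets the scope of the liver summary: "markedly abnormal liver function-related laboratory tests will be summarized during all visits in the study based on the criteria listed below in Table C". The table named there holds the ALT, AST and bilirubin thresholds and the Hy's Law components. SAP 15.3 states no post-baseline or on-treatment limit.

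SAP 6.5 has a general rule for the same kind of determination: "no values will be excluded from listings or for the determination of markedly abnormal laboratory (unless outside the defined in-treatment period"). The on-treatment period in SAP 6.5 and Table B is defined as "From Day 1 until ≤14 days after last tablet intake".

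Protocol 9.4.3.2 specifies the quantity to report: "The incidence of post-baseline markedly abnormal values will be presented based on categories to be identified in the SAP". The text under protocol Table 11 says that "no values will be excluded from the determination of markedly abnormal laboratory or vital signs values", with the bracketed limit "unless outside the defined in-treatment period". Footnote a to that table defines the period as "From Day 1 until ≤ 28 days after last tablet intake".

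SAP 3.2 declares the move from 28 to 14 days as a correction. Its reason is that the follow-up visit occurs 14 days, plus up to 5, after the last tablet. It declares no widening of the laboratory summary to pre-drug visits.

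**The concern.** Two SAP sections give different scopes for one determination, and nothing says which governs. Under 15.3 a screening value can enter the summary. Under 6.5 it cannot, but a value from an on-schedule V7 can be lost.

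Laboratory abnormalities are part of the primary safety endpoint (SAP Table A), and Table C is the only markedly abnormal laboratory criterion that the SAP text states. There is no comparator arm. A pre-drug liver value counted in this summary could be read as a finding on NOMAC-E2, and a V7 value left out would hide one. For rare liver events, including Hy's Law combinations, one woman can change what the report says.

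The schedule makes both errors possible. Routine chemistry is planned only at V1 and at V7/ET (protocol Schedule of Activities and 9.4.3.2). A woman with a raised first screening result can still be dosed if a retest is acceptable: "Screening laboratory safety tests may be repeated once before treatment allocation (V2) at the discretion of the Investigator" if the first results do not fit her clinical status or recent laboratory results. Her first value would still meet Table C.

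**Working it through.** **Inputs**

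- Treatment: 13 cycles of 28 days, with 24 active tablets per cycle (protocol 6.1).
- V7/ET: 14 to 19 days after the last intake (Schedule of Activities, window +5; protocol 8.4.1).
- Period end, SAP 6.5 and Table B: last tablet + 14 days.
- Period end, protocol Table 11 footnote a: last tablet + 28 days.
- Period start in both tables: Day 1.

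SAP 6.5 writes in-treatment in the bracket but defines only an on-treatment period. I take these to be the same.

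**Step 1: days for a completer**

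- Last tablet = 13 × 28 = Day 364.
- Permitted V7 days = 364 + 14 to 364 + 19 = Days 378 to 383, which is 6 days.
- SAP period ends on 364 + 14 = Day 378. Kept: Day 378 only, 1 of 6.
- Protocol Table 11 period ends on 364 + 28 = Day 392. Kept: 6 of 6.

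The result does not depend on Day 364. For any last-tablet day L, the visit may fall on L + 14 to L + 19 and the SAP keeps only L + 14, so it applies equally to early-termination visits held on schedule.

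**Step 2: Table B's own visit window**

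Table B places V7 at 379 ± 14, which is Days 365 to 393. That window covers all six permitted days. The loss comes from the on-treatment limit, not from the visit window.

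**Step 3: three illustrative records**

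Each is a completer with last tablet on Day 364. *Protocol* means post-baseline within the Table 11 period.

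| Record | SAP 15.3, literal | SAP 6.5 | Protocol |
|---|---|---|---|
| A. First screening ALT 3.4 × ULN, retest normal, dosed, V7 normal | counted | not counted | not counted |
| B. Screening normal, V7 on Day 381 with ALT 3.4 × ULN | counted | not counted | counted |
| C. As B, but V7 on Day 378 | counted | counted | counted |

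SAP 15.3 differs from the protocol on A. SAP 6.5 differs on B, and only because 381 exceeds 378 but not 392.

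**The case against.** The strongest reply is that SAP 6.5 is the protocol's rule. The text under protocol Table 11 has the same in-treatment limit in nearly the same words, and both periods begin on Day 1, so every value that 6.5 admits is post-baseline. This stands. A reader might infer that neither SAP rule matches the protocol, or that any in-treatment limit is a departure. The documents do not support that: 6.5 departs only through its earlier end date.

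A reader might also infer that this departure is undeclared. It is declared, in SAP 3.2. What 3.2 does not do is carry its reason through: it cites a visit at 14 (+5) days and then sets an end that leaves out the 5.

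The protocol is not tidy either. The body of 9.4.3 ends the on-treatment period 14 days after the last *active* tablet. For a completer that is 12 × 28 + 24 = 360, and 360 + 14 = Day 374, before any permitted V7 day. But the limit on markedly abnormal values uses the in-treatment term, and Table 11 footnote a defines that period with 28 days.

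SAP 15.3 also has milder readings. Its scope may mean only that visit windows are ignored. The output may be by visit, with screening in its own row. The SAP's modification history removes a markedly abnormal table and adds a listing for liver tests, where dates would reveal pre-drug values. All are possible, and the output templates are not available here to settle it. The text of 15.3 states none of them and still describes a summary.

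Finally, Hy's Law-type events are also events of clinical interest, summarised as TEAEs, which exclude pre-treatment onset. That protects the event-of-clinical-interest summary but not the Table C summary.

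**Conclusion.** The point holds in limited form. SAP 15.3 and 6.5 conflict over screening values, and 15.3 read literally goes beyond the post-baseline incidence that the protocol asks for. Separately, the 14-day end keeps 1 of the 6 permitted V7 days, where protocol Table 11 kept all 6, although V7/ET is the only scheduled post-baseline liver panel.

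One of six days does not mean one of six women. The documents give no distribution of actual visit days, and visits may cluster on the target day.

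It is tempting to put a percentage on the inflation from screening values, or to argue that half or more of the scheduled panels are pre-drug. Neither measures bias. An inflation figure needs the rate of marked values per panel and the share of women with a marked screening value who are still dosed, and the documents give neither. Exclusion criterion 25 removes women whose screening results the investigator judges clinically relevant, so pre-drug hits among treated women should be rare. The issue is a handful of cases at most, in a summary where a single case can matter.

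The conclusion assumes that 15.3 is applied as written and that in-treatment in SAP 6.5 means the period defined in that section.

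**What to change.** 1. In SAP 15.3, replace the all-visits scope with post-baseline values from the first tablet through V7/ET, including unscheduled values.
2. Show any pre-drug value meeting Table C separately, as baseline.
3. In SAP 6.5 and Table B, set the period end used for the markedly abnormal determination to last tablet + 19 days, so that it covers the whole V7 window.
4. Correct SAP 3.2 to match, so that the declared reason and the period agree.

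The cost is a few sentences of SAP text and one programming flag, with no new data. The small downside is that values taken 15 to 19 days after the last tablet enter the summary. They can be flagged by days since last tablet. The 14-day rule for TEAEs need not change.
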